10.4.4 Analysis of Safety Endpoints

The safety parameters to be assessed are described in [Section 7.8](#) Displays for safety results will utilize descriptive statistics. No formal hypothesis testing of safety data is planned.

Adverse events will be coded using the Medical Dictionary for Regulatory Activities (MedDRA). Incidence of each body system and preferred term will be tabulated for each treatment group. Treatment-emergent adverse events (TEAE) are defined as those reported on or after the first dose of study drug through 28 days from the last dose of study drug. Summaries will include all TEAEs, TEAEs

considered related to study treatment by investigators, Graded TEAEs, and SAEs. All AEs, emergent or non-emergent, will be listed by subject. Any TEAEs leading to premature discontinuation from the study intervention and serious TEAEs will be presented by listing.

Clinical laboratory results will be summarized descriptively by treatment group including values, changes from Baseline, and incidence of laboratory abnormalities. Laboratory results will be listed for each subject.

Vital sign data and ECG findings reported at each visit will be displayed by treatment, using descriptive statistics for observed and change from Baseline values.

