1. INTRODUCTION

Study ABI-H2158-201 is a Phase 2a, multicenter, randomized, single-blind, placebo (PBO)-controlled, multiple cohort study evaluating ABI-H2158-containing regimens in chronic hepatitis B virus (HBV) infection (cHBV). The target population is male or female subjects with cHBV, 18 to 65 years of age, inclusive, with no evidence of cirrhosis or end-stage liver disease. Cohort 1 will enroll treatment-naïve subjects with hepatitis B virus “e” antigen (HBeAg) positive cHBV. Cohort 2 will enroll treatment-naïve subjects with HBeAg negative cHBV.

This statistical analysis plan (SAP) describes the statistical analysis methods and data presentations to be used in tables, figures, and listings (TFLs) in the clinical study report (CSR) for Study ABI-H2158-201. This SAP is based on the Study Protocol Amendment 2, dated 14 December 2020; UK country-specific protocol amendment, dated 17 December 2020; Korea-country specific protocol amendment, dated 05 February 2021; ABI-H2158-201 Protocol Clarification Letter for Amendment 2; dated 14 Dec 2020, 07 September 2021; and the electronic case report form (eCRF). On 01 September 2021, Assembly made the decision to discontinue the development of ABI-H2158 following the observation of elevated alanine aminotransferase (ALT) levels consistent with drug-induced liver injury (DILI) in study ABI-H2158-201. Therefore, only key safety and efficacy endpoints will be performed. The SAP will be finalized before final database lock. Any changes made after the finalization of the SAP will be documented in the Synoptic CSR.

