7. SAFETY ANALYSES

7.1. Adverse Events and Deaths

7.1.1. Adverse Event Dictionary

Clinical and laboratory adverse events (AEs) will be coded using the Medical Dictionary for Regulatory Activities (MedDRA) v23.0. System organ class (SOC), high-level group term (HLGT), high-level term (HLT), preferred term (PT), and lower-level term (LLT) will be provided in the AE dataset.

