7.1.6. Summaries of Adverse Events and Deaths

Treatment emergent AEs will be summarized based on the Safety Analysis Set.

A brief, high-level summary of the number and percentage of subjects who experienced at least 1 TEAE in the categories described below will be provided by treatment group. In addition, a table for each category showing the number and percentage of subjects will be provided by PT and treatment group in descending order of total frequency:

- TEAEs
- TEAEs by severity grade
- TE SAEs
- TEAEs leading to ABI-H2158/PBO discontinuation
- TEAEs leading to ETV discontinuation
- TEAEs leading to study discontinuation
- TEAEs related to ABI-H2158/PBO
- TEAEs related to ETV
- TE SAEs related to ABI-H2158/PBO
- TE SAEs related to ETV
- COVID-19 specific TEAEs
- COVID-19 specific TE SAEs

Multiple events will be counted only once per subject in each summary. For summary by severity grade, the most severe grade will be used for those AEs that occurred more than once in an individual subject during the study.

A brief, high-level summary of the number and percentage of subjects who experienced at least 1 off-treatment AE in the same categories as the TEAEs except for the AEs leading to ABI-H2158/PBO discontinuation will be provided by treatment group. In addition, a table for each category showing the number and percentage of subjects will be provided by PT and treatment group in descending order of total frequency. The off-treatment AEs are counted starting from 29 days after the last dose of ABI-H2158/PBO.

A data listing containing all AEs will be provided.

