7.2.2.2. ALT Elevation with Declining Hepatic Function

A confirmed ALT elevation with evidence of declining hepatic function is defined as meeting the following criteria at 2 consecutive visits:

- ALT elevation $\geq 2 \times \text{Baseline (Day 1)}$ or nadir and $> 2 \times \text{ULN(Covance)}$ AND
- Direct bilirubin increase to $\geq 2 \times \text{Baseline (Day 1)}$ and $\geq 2 \times \text{ULN(Covance)}$ OR
- Albumin decline $\geq 0.5 \text{ g/dL}$ OR $\text{INR} > 2 \times \text{Baseline (Day 1)}$ OR
- Symptoms of liver inflammation (eg, fatigue, weakness, lack of appetite, nausea, vomiting, jaundice or discolored feces)

The number and subjects meeting the above laboratory criteria will be summarized by treatment group. Clinical signs or symptoms of liver inflammation will not be included in the summary. For individual laboratory tests, subjects will be counted once based on the most severe postbaseline values. For the composite criteria, subjects will be counted once when the criteria are met at the same visit. The denominator is the number of subjects in the Safety Analysis Set who have nonmissing postbaseline values. A listing of subjects who met at least 1 of the above criteria will be provided.

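### SAP 7.1.6 drops the protocol's body-system level from the adverse-event tables without saying so, and no adverse-event table counts subjects with at least one hepatic event

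*Combined protocol and SAP*

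**What the plan says.** Protocol 10.4.4 sets the level of AE tabulation: "Incidence of each body system and preferred term will be tabulated for each treatment group".

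SAP 7.1.6 opens with "A brief, high-level summary of the number and percentage of subjects who experienced at least 1 TEAE in the categories described below". It then plans, for each of those categories, a table "showing the number and percentage of subjects will be provided by PT and treatment group in descending order of total frequency". The off-treatment AE tables follow the same layout. There are 12 TEAE categories. The only two defined by topic are for COVID-19, and none is hepatic.

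SAP 7.1.1 codes system organ class and the intermediate MedDRA levels, but says only that they "will be provided in the AE dataset". No table uses them.

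SAP 1 records that development stopped "following the observation of elevated alanine aminotransferase (ALT) levels consistent with drug-induced liver injury (DILI) in study ABI-H2158-201".

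The SAP also plans liver laboratory summaries. SAP 7.2.1.2 counts subjects by worst treatment-emergent grade for each test and repeats the summary for the off-treatment period. SAP 7.2.2.2 adds: "The number and subjects meeting the above laboratory criteria will be summarized by treatment group". It then limits this: "Clinical signs or symptoms of liver inflammation will not be included in the summary".

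**The concern.** There are two separate points.

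The first is a mismatch. The protocol promises two levels of tabulation and the SAP delivers one. SAP 6.2, the section on changes from the protocol, deals with efficacy only. The general cut in scope after termination (SAP 1) does not mention AE tables, and the SAP keeps 12 TEAE categories with PT tables.

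The second is a gap. A reader of the report will want to know how many subjects per arm had a hepatic AE, and how many of those events were serious, judged related, or led to stopping ABI-H2158 or placebo. Hepatic events can be coded to several preferred terms, and a subject with two such terms appears in two rows. The planned AE tables therefore give no direct answer on the topic that ended development, in a trial where the proportion of subjects with AEs is part of a primary endpoint (protocol 3.2.1).

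**Working it through.** There is no design figure to reproduce: the sample size is stated not to rest on statistical considerations. The check is a comparison of texts, followed by bounds on what PT rows can tell a reader.

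**Texts side by side**

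| Item | Protocol 10.4.4 | SAP |
|---|---|---|
| Level of AE tables | Body system and PT | PT only (7.1.6) |
| Body-system coding | – | Dataset only (7.1.1) |
| Change declared | – | No; 6.2 covers efficacy |
| Grouped hepatic AE count | Not promised | Not planned |

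**Bounds.** Take PT counts c1, c2, … in an arm of N subjects. The number of subjects with at least one of these events lies between max(c) and min(sum of c, N).

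**Check against protocol Table 3** (earlier study, 100 mg arm, N = 7):
- Five PT entries (headache, dizziness, upper abdominal pain, rash, fatigue), one subject each. Bounds: 1 to 5. The table's any-event row gives 3 (3/7 = 42.9%). The rows sum to 5, so adding them overstates the number of subjects.
- Nervous system: headache 1 and dizziness 1. Bounds: 1 to 2. The body-system row settles it at 2 (2/7 = 28.6%). This is the information a PT-only table loses.

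**The same limit in by-test laboratory tables** (protocol Table 4):
- 100 mg arm: AST 2, ALT 2. Subjects with either: 2 to 4.
- 300 mg arm: AST 1, ALT 2. Subjects with either: 2 to 3.

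**Illustration for this trial.** N = 30 is the planned active arm of one cohort. The PT counts are assumed, because the documents give no AE counts for this trial.

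| Assumed liver PT counts | Subjects possible | Rate |
|---|---|---|
| 2, 2, 2 | 2 to 6 | 6.7% to 20.0% |
| 3, 2, 1 | 3 to 6 | 10.0% to 20.0% |
| 1, 1, 1, 1 | 1 to 4 | 3.3% to 13.3% |

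**Would body system alone close the gap?** No. Protocol Table 3 files ALT increase under Investigations, not under a hepatic class. A body-system table would leave such terms apart from any liver diagnosis, so a grouped row is needed as well.

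**The case against.** The strongest reply is that liver injury is covered at subject level by laboratory data, which may be the better measure. Graded tables start at 1.25 x ULN for ALT and AST (protocol Appendix 2). SAP 7.2.2.2 starts at 2 x Baseline or nadir and above 2 x ULN, counts composite cases once, and comes with a subject listing. Under protocol 8.5 a laboratory abnormality becomes an AE only if the investigator judges it clinically significant. In the earlier study, 4 of 14 active subjects (28.6%) and 1 of 4 placebo subjects (25%) had Grade 1 ALT elevations, yet Table 3 shows ALT increase as an AE in no active subject and one placebo subject. An AE count of ALT terms alone would have pointed the wrong way. The report is also to be synoptic, an all-AE listing is planned, and neither document promises a grouped hepatic count.

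Much of this stands. It rules out reading the laboratory summaries as absent or as limited to high thresholds: only SAP 7.2.2.1 uses 10 x ULN. It also means a hepatic AE row should be read with the laboratory tables, not in place of them.

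It does not close the gap. The laboratory summaries run by test or by laboratory composite. They carry no seriousness, relatedness or discontinuation, and SAP 7.2.2.2 omits symptoms from its count. A count rebuilt from the listing would rest on terms chosen after seeing the data. Nor does any of it explain the undeclared departure from protocol 10.4.4.

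**Conclusion.** Two things hold. SAP 7.1.6 departs from protocol 10.4.4 by tabulating AEs by preferred term only, and does not say so. Separately, no AE table counts subjects with at least one hepatic AE, so the planned tables only bound that rate. In the assumed example of three PTs with 2 subjects each among 30, the upper bound is three times the lower (20.0% against 6.7%).

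A reader might infer more, and the documents do not support it:
- That no table counts liver events at all. SAP 7.2.1.2 and 7.2.2 count subjects by liver laboratory criteria.
- That losing body system is what removes the liver count. The protocol's own table would not have supplied one, as the filing of ALT increase under Investigations shows.
- That hepatic AEs in this trial were in fact scattered over several terms. That is a reasonable expectation from how such events are coded, but no AE counts for this trial are given.

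The severity is minor. The data are collected and coded, and subject-level information survives in the listing.

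**What to change.** 1. Restore the body-system-by-PT table that protocol 10.4.4 specifies, or state in the SAP that it is dropped and why.
2. Add a row counting each subject once for any hepatic AE, by treatment group, for these categories: any AE, severity grade, serious, related, and leading to discontinuation of ABI-H2158 or placebo. Do this for TEAEs and, except for the discontinuation category, for off-treatment AEs, matching the existing layout of SAP 7.1.6.
3. Define hepatic AE by a standard MedDRA hepatic grouping or a list of preferred terms, fixed by the blinded team before database lock and unblinding. This is feasible under the SAP: it is to be finalized before final lock (SAP 1), and the study stays blinded outside the Data Review Committee (SAP 2.1).
4. State that the row is to be read alongside the SAP 7.2.1.2 and 7.2.2 summaries, because AE reporting of laboratory changes depends on investigator judgement.

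The cost is SAP wording and one extra table shell. No new data are needed, since system organ class and preferred term are already in the AE dataset.

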7.2. Laboratory Evaluations

Laboratory data collected during the study will be analyzed and summarized using both quantitative and qualitative methods based on the Safety Analysis Set. The laboratory values that are below LLOQ or above the upper limit of quantitation will be listed as such, and the closest imputed value will be used for the purpose of calculating summary statistics as specified in [Section 3.4](#).

7.2.1. Graded Laboratory Values

The criteria specified in the study protocol will be used to grade laboratory results as normal (Grade 0), mild (Grade 1), moderate (Grade 2), severe (Grade 3) or potentially life threatening (Grade 4). See Protocol Appendix 2 for detailed DAIDS grading criteria on the relevant laboratory tests. Grade 0 includes all values that do not meet the criteria for an abnormality of at least Grade 1. For laboratory tests with criteria for both increased and decreased levels, analyses for each direction (ie, increased, decreased) will be presented separately.

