AFP: alpha fetoprotein; ALT: alanine aminotransferase; aPTT: activated partial thromboplastin time; AST: aspartate aminotransferase; FSH: follicle-stimulating hormone; GGT: gamma-glutamyl transpeptidase; HAV: hepatitis A virus; HbA1c: hemoglobin A1c; HCV: hepatitis C virus; HDV: hepatitis D virus; HEV: hepatitis E virus; HIV: human immunodeficiency virus; IgM: immunoglobulin M; INR: International Normalized Ratio; LDH: lactate dehydrogenase; MCHC: mean corpuscular hemoglobin concentration; MCV: mean corpuscular volume; RBC: red blood cell; ULN: upper limit of normal.

^a Perform fractionated bilirubin if total bilirubin >ULN.

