 - If ALT is rising at the confirmatory visit, subjects should return for an Unscheduled Visit every 2 to 5 days until the ALT elevation has stabilized. At these visits, the following laboratory tests will be performed: ALT, AST, total bilirubin (if total bilirubin is elevated, reflex to direct bilirubin), serum albumin, INR, creatine kinase, HBV DNA, quantitative HBV serologies (HBeAg [reflex to qualitative HBeAg if quantitative HBeAg is negative] and HBsAg [reflex to qualitative HBsAg if quantitative HBsAg is negative]). The Investigator will determine if other Unscheduled Visit assessments should be performed. Subjects whose ALT has stabilized should continue to be monitored weekly (or more frequently, as deemed necessary by the treating physician) until ALT values return to normal or Baseline levels.
- ALT Elevation with Declining Hepatic Function
 - Subjects with confirmed ALT elevation with evidence of declining hepatic function should be discontinued from study treatment. This is defined as:
 - ALT elevation $\geq 2 \times$ Baseline (Day 1) or nadir and $> 2 \times$ ULN AND
 - Direct bilirubin increase to $\geq 2 \times$ Baseline (Day 1) and $\geq 2 \times$ ULN OR
 - Albumin decline ≥ 0.5 g/dL OR INR $> 2 \times$ Baseline (Day 1) OR
 - Symptoms of liver inflammation (eg, fatigue, weakness, lack of appetite, nausea, vomiting, jaundice or discolored feces)
 - Subjects with evidence of declining hepatic function should return for an Unscheduled Visit every 2 to 5 days until the relevant laboratory values stabilize. Subjects whose hepatic function has stabilized should continue to be monitored weekly (or more frequently as deemed necessary by the Investigator) until the relevant laboratory values return to normal or Baseline (Day 1).

[figure not shown]
All subjects with ALT elevation with or without declining hepatic function should continue to be followed on their regular study visit schedule, with the addition of Unscheduled Visits as described above. If the post-treatment ALT elevation has not substantially resolved by the last study follow-up visit, subjects should continue to return to clinic as deemed medically appropriate by the Investigator, in consultation with the Sponsor. The Unscheduled Visit module in the case report form should be utilized as needed to gather additional clinical and laboratory data until the ALT elevation is documented to be

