Injection Site Induration or Swelling Report only one	Same as for Injection Site Erythema or Redness , >15 years of age	Same as for Injection Site Erythema or Redness , >15 years of age	Same as for Injection Site Erythema or Redness , >15 years of age	Same as for Injection Site Erythema or Redness , >15 years of age
Injection Site Pruritus	Itching localized to the injection site that is relieved spontaneously or in <48 hours of treatment	Itching beyond the injection site that is not generalized OR Itching localized to the injection site requiring ≥48 hours treatment	Generalized itching causing inability to perform usual social & functional activities	NA

¹² Injection Site Erythema or Redness should be evaluated and graded using the greatest single diameter or measured surface area.

Laboratory Values*: Chemistries				
Parameter	Grade 1 Mild	Grade 2 Moderate	Grade 3 Severe	Grade 4 Potentially Life-Threatening
Acidosis	NA	pH≤7.3 to <LLN	pH<7.3 without life- threatening consequences	pH<7.3 with life- threatening consequences
Albumin, Low (g/dL; g/L)	3.0 to <LLN 30 to <LLN	≥ 2.0 to <3.0 ≥ 20 to <30	< 2.0 < 20	NA
Alkaline Phosphatase, High	1.25 to < 2.5 x ULN	2.5 to < 5.0 x ULN	5.0 to < 10.0 x ULN	≥ 10.0 x ULN
Alkalosis	NA	pH > ULN to □ 7.5	pH > 7.5 without life- threatening consequences	pH > 7.5 with life- threatening consequences
ALT or SGPT, High Report only one	1.25 to < 2.5 x ULN	2.5 to < 5.0 x ULN	5.0 to < 10.0 x ULN	≥ 10.0 x ULN
Amylase (Pancreatic) or Amylase (Total), High Report only one	1.1 to <1.5×ULN	1.5 to <3.0×ULN	3.0 to <5.0×ULN	≥5.0×ULN
AST or SGOT, High Report only one	1.25 to < 2.5 x ULN	2.5 to < 5.0 x ULN	5.0 to < 10.0 x ULN	≥ 10.0 x ULN
Bicarbonate, Low (mEq/L; mmol/L)	16.0 to <LLN 16.0 to <LLN	11.0 to <16.0 11.0 to <16.0	8.0 to <11.0 8.0 to <11.0	<8.0 <8.0
Bilirubin Direct Bilirubin, High	NA	NA	> ULN with other signs and symptoms of hepatotoxicity.	> ULN with life- threatening consequences (eg, signs and symptoms of liver failure)
Total Bilirubin, High	1.1 to <1.6×ULN	1.6 to <2.6×ULN	2.6 to <5.0×ULN	≥5.0×ULN
Calcium, High (mg/dL; mmol/L)	10.6 to <11.5 2.65 to <2.88	11.5 to <12.5 2.88 to <3.13	12.5 to <13.5 3.13 to <3.38	≥3.5 ≥3.38
Calcium (Ionized), High (mg/dL; mmol/L)	>ULN to <6.0 >ULN to <1.5	6.0 to <6.4 1.5 to <1.6	6.4 to <7.2 1.6 to <1.8	≥7.2 ≥1.8
Calcium, Low (mg/dL; mmol/L)	7.8 to <8.4 1.95 to <2.10	7.0 to <7.8 1.75 to <1.95	6.1 to <7.0 1.53 to <1.75	<6.1 <1.53

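### A direct bilirubin above ULN with no clinical qualifier attached is tabulated as Grade 0 (normal), and no by-arm count covers elevations outside the SAP 7.2.2.2 threshold

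*Combined protocol and SAP*

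**What the plan says.** **Grading scale.** In the chemistry table of protocol Appendix 2, direct bilirubin is not applicable at Grades 1 and 2. Grade 3 is "> ULN with other signs and symptoms of hepatotoxicity". Grade 4 is a value above ULN with life-threatening consequences. Total bilirubin, by contrast, is graded on numbers alone, starting at "1.1 to <1.6×ULN".

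**How the SAP applies it.** SAP 7.2.1 uses the protocol criteria to "grade laboratory results as normal (Grade 0), mild (Grade 1), moderate (Grade 2), severe (Grade 3) or potentially life threatening (Grade 4"), and adds that "Grade 0 includes all values that do not meet the criteria for an abnormality of at least Grade 1". Under SAP 7.2.1.1 an abnormality is treatment-emergent only if the value rises by at least one grade from Baseline, up to 28 days after the last dose of ABI-H2158/PBO (any Grade 1 or higher counts if Baseline is missing). SAP 7.2.1.2 tabulates the worst grade over that window, and separately the off-treatment period from day 29.

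**Where direct bilirubin is used numerically.** Protocol 9.4 includes, jointly with an ALT elevation, "Direct bilirubin increase to $\geq 2 \times$ Baseline (Day 1) and $\geq 2 \times$ ULN" among the indications of declining hepatic function. SAP 7.2.2.2 repeats this criterion, summarizes it by treatment group, and says "For individual laboratory tests, subjects will be counted once based on the most severe postbaseline values". It also says "Clinical signs or symptoms of liver inflammation will not be included in the summary".

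**The concern.** A reader of the graded laboratory table will take Grade 0 to mean that the result was normal, because SAP 7.2.1 says so. For direct bilirubin it can also mean that the result was raised but no clinical finding was linked to it. A row of zeros could then be read as no elevations when it shows only that none could be graded.

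This matters more here than in most trials. Abnormal laboratory results are part of a primary endpoint (protocol 3.2.1), and SAP section 1 records that development stopped after ALT rises consistent with drug-induced liver injury. The protocol itself relies on the direct fraction: exclusion criterion 13 sets a limit on it and uses it to decide eligibility in Gilbert's syndrome, where total bilirubin may be raised at entry.

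**Working it through.** No sample size, alpha or power is involved, and the plan gives no figure to reproduce. The check applies the stated rules to a range of values.

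**1. Grades by rule.** Inputs: the Appendix 2 bilirubin rows, the SAP 7.2.1 Grade 0 rule, and the 2x ULN part of the 9.4 criterion. Each multiple refers to the analyte's own ULN.

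| Multiple of ULN | Direct, no qualifier | Direct, with signs/symptoms | Direct, life-threatening | Reaches 2x ULN | Total at same multiple |
|---|---|---|---|---|---|
| 1.05 | 0 | 3 | 4 | no | 0 |
| 1.2 | 0 | 3 | 4 | no | 1 |
| 2 | 0 | 3 | 4 | yes | 2 |
| 3 | 0 | 3 | 4 | yes | 3 |
| 5 | 0 | 3 | 4 | yes | 4 |
| 10 | 0 | 3 | 4 | yes | 4 |

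The size of the elevation does not affect the direct-bilirubin grade. Only the clinical qualifier does, and the SAP does not say who or what attaches it, or whether a raised ALT or INR is a sign. The same record can be Grade 0 or Grade 3 depending on a programming choice.

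**2. What SAP 7.2.2.2 recovers.** It needs both at least 2x Baseline and at least 2x ULN.
- Values from above ULN to below 2x ULN fail the ULN part.
- If Baseline is above ULN, the Baseline part is the stricter one. Exclusion 13d admits direct bilirubin up to 1.2x ULN at Screening. If Baseline equals that, the threshold is 2 x 1.2 = 2.4x ULN, so values from 2.0x to below 2.4x ULN are not counted.
- The confirmed definition also requires two consecutive visits.

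**3. What total bilirubin recovers.** The documents give no reference limits, so this step rests on assumptions. With direct bilirubin at exactly 2x its ULN:

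total as a multiple of ULN = (2 x direct ULN + indirect) / total ULN

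The assumed limits (direct/total ULN, mg/dL) are 0.2/1.2, 0.3/1.2, 0.4/1.0 and 0.4/1.2, each with indirect bilirubin of 0.3, 0.5 and 0.8.
- Lowest: (0.4 + 0.3)/1.2 = 0.58x ULN, Grade 0.
- Highest: (0.8 + 0.8)/1.0 = 1.6x ULN, Grade 2.
- Seven of the twelve combinations leave total bilirubin at Grade 0. In six of these, total does not exceed its ULN. In the seventh, (0.8 + 0.5)/1.2 = 1.08x ULN, above ULN but below the 1.1x cut.

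These counts illustrate the range; they are not probabilities. They also depend on when direct bilirubin is measured. Footnote a to protocol Table 5 says "Perform fractionated bilirubin if total bilirubin >ULN". If direct bilirubin is measured only by that reflex, the six combinations yield no direct result at all, and only totals between 1.0x and 1.1x ULN are fractionated yet ungraded.

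**The case against.** The strongest reply has five parts.

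- **Grades 3 and 4 exist and can be reached.** A reader might infer that the direct-bilirubin row is empty by construction, or that every elevation in both arms is reported as normal. The documents do not support that. Protocol 8.2 has the Investigator grade laboratory abnormalities against Appendix 2, so someone is in a position to apply the qualifier. SAP 7.2.1 neither requires nor excludes grading from values alone. This stands, and limits the point to elevations with no qualifier attached.
- **The qualifier is broader than symptoms.** It covers signs, which are undefined, and subjects meeting 9.4 also have an ALT elevation that might count. This also stands, but it shows that a derivation rule is missing.
- **Protocol 9.4 and Appendix 2 need not agree.** A reader might infer a contradiction. But 9.4 uses direct bilirubin only together with ALT, and a toxicity scale and a management criterion may use different thresholds. No contradiction is claimed.
- **The data are reported elsewhere.** SAP 7.2.2.2 counts and lists subjects; SAP 7.2 promises quantitative as well as qualitative methods; protocol 10.4.4 plans values and changes; SAP 3.4 has a numeric rule for low direct bilirubin; and the SAP 7.2.1.2 listing shows all results for the test of interest. The information is therefore not lost. But means, changes and by-subject listings do not give the number of subjects per arm with an elevation.
- **Total bilirubin is graded from 1.1x ULN.** This catches many cases, especially under reflex measurement. Gilbert's syndrome is an argument about specificity: a raised total over-flags those subjects, and does not show that injury is missed.

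**Conclusion.** The point holds in a limited form. Under Appendix 2 and SAP 7.2.1, a direct bilirubin above ULN without the clinical qualifier is labelled normal at every multiple of ULN and can never be treatment-emergent. The SAP leaves open how the qualifier is attached. Only if grading is run on laboratory values alone would the row be empty, and that condition is not stated in the plan.

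With the other outputs credited, the gap is a by-arm count of isolated elevations in two ranges: between ULN and 2x ULN, and at least 2x ULN but below 2x Baseline. The second range requires a Baseline above ULN. The number of subjects affected is unknown; it depends on the reference limits, on whether direct bilirubin is measured routinely or by reflex, and on how grading is programmed. The defect concerns how one analyte is reported within a primary safety endpoint. It is worth correcting because of the liver signal that ended development and because the correction is small.

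**What to change.** In SAP 7.2.1.2:

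1. Do not present a direct bilirubin above ULN as Grade 0, normal.
2. Add a row by treatment group giving the worst postbaseline direct bilirubin as <=ULN, >ULN to <2x ULN, and >=2x ULN. Use subjects with a measured value as the denominator, and the same on-treatment (through 28 days after last dose) and off-treatment (from day 29) windows as the graded table.
3. Keep any Appendix 2 Grade 3 or 4 that is assigned with the clinical qualifier, and state how that qualifier is attached to the laboratory record. Deleting these categories is unnecessary and would remove the most serious ones.
4. Footnote the graded table to the SAP 7.2.2.2 summary.

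The cost is a short SAP addition and one extra table row, from results already collected; no clinical rule changes. The drawback is the denominator: if direct bilirubin is measured only by reflex, it is limited to subjects whose bilirubin was fractionated, and the row should say so.
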